
Accelerometer (gold standard), Self-reported questionnaires (IPAQ, CHAMPS) Neurocognitive measures: Questionnaires (Mini Cog, Falls risk), Short Physical Performance Battery Quality of Life: SF-12 Bowels: Birmingham 8 WEEK FOLLOW-UP VISIT: Physical activity: Accelerometer (gold standard), Self-reported questionnaires (IPAQ, CHAMPS) Neurocognitive measures: Questionnaires (Mini Cog, Falls risk follow up), Short Physical Performance Battery Quality of Life: SF-12 Urinary: Questionnaires (OABq-SF, UDI-6) Adherence: Questionnaires (Belief in Medication follow up questionnaire, MASRI), pill count Patient Global Index of Improvement (PGI-I) form Bowels: Birmingham Qaseem A, Dallas P, Forciea MA, Starkey M, Denberg TD, Shekelle P; Clinical Guidelines Committee of the American College of Physicians. Nonsurgical management of urinary incontinence in women: a clinical practice guideline from the American College of Physicians. Ann Intern Med. 2014 Sep 16;161(6):429-40. Ellsworth PI. The pharmacologic management of idiopathic overactive bladder in primary care. J Fam Pract. 2014 Feb;63(2 Suppl):S38-45. Review. Association of Reproductive Health Professionals. A Quick Reference Guide for Clinicians: Diagnosis and Management of Overactive Bladder. <https://www.arhp.org/uploadDocs/OABQRG.pdf>. Assessed 6.5.2015

Study duration

Penn Urogynecology has an established track record of successfully recruiting adults with OAB into cohort studies and randomized control trials. We plan to recruit 13 to 14 patients per month to reach target enrollment of 80 patients by 6 months. As in most clinical trials of OAB, we anticipate that two-thirds of recruited subjects will be female. Patients will be followed for a total of 8 weeks (see Design). Ideally, we would start subject recruitment in March 2016, and subject recruitment and data collection would be finished in September of 2016.

Resources necessary for human research protection

Describe research staff and justify that the staff are adequate in number and qualifications to conduct the research. Describe how you will ensure that all staff assisting with the research are adequately informed about the protocol and their research related duties. Please allow adequate time for the researchers to conduct and complete the research. Please confirm that there are adequate facilities for the research.

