
Characteristics of the Study Population

Target population

Adult subjects aged 65 or older with overactive bladder undergoing treatment with medication

Subjects enrolled by Penn Researchers

80

Subjects enrolled by Collaborating Researchers

0

Accrual

Recruitment/Retention Experience: The urogynecology/urology clinics of the Hospital of University of Pennsylvania are high volume referral clinics staffed by four urogynecologists and one urologist. We see 125 female and 50 male patients with OAB per month with eligibility:participation ratio of 1.5:1 in clinical trials. In recent trials, 50% of recruited adults were Caucasian and 45% African-American. We anticipate that the female:male ratio will be 2:1. Sample Size: Specific Aim 1: A sample size of 68 evaluable subjects will provide 90% power to detect a correlation coefficient of 0.72 or greater, assuming a correlation coefficient of 0.5 or less between the physical activity questionnaires and the criterion standard (accelerometer) is undesirable (null hypothesis). Assuming a 15% loss to follow-up, we plan to enroll 80 patients to ensure an adequate sample of at least 68 subjects with complete datasets. Specific Aim 2: We have conservatively assumed that 50% subjects will express preference for medication. Prior Penn studies show 56% adherence at 8 weeks in unselected subjects. Assuming that adherence will be 80% in subjects expressing preference for medication, a sample size of 80 subjects will provide 90% power to demonstrate a 30% difference in adherence rates in subjects who do or do not have preference for medication. Specific Aim 3: Assuming two-tailed alpha of 0.05, a sample size of 80 subjects will provide 90% power to show a 30% difference in physical activity in the proportion of subjects expressing preference for medication versus those without preference.

Key inclusion criteria

Inclusion Criteria: adults aged 65 or older, urinary urgency of quite a bit severity or more on the Overactive Bladder Questionnaire-Short Form (OABq-SF),⁵⁰ who are eligible for pharmacologic therapy for overactive bladder

Key exclusion criteria

Exclusion Criteria: predominant stress incontinence (on UDI-6), current/recent use (6 m) or contraindication to anti-cholinergic medication, severe voiding difficulties, men on 5-alpha reductase inhibitors, severe neurologic disease, recent anti-incontinence or prolapse surgery, other urinary tract conditions such as calculus or recurrent UTI.

Vulnerable Populations

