Analysis Plan Specific Aim 1 and 2: We will evaluate physical activity, adherence, and neurocognitive function before and after treatment to examine changes from baseline to 8 weeks in subjects with and without preference for medication. Concurrent validity, the relationship of the instrument to other similar evaluations, will be measured by comparing IPAQ, and CHAMPS scores to accelerometer data at baseline using the Spearman correlation coefficient and the intraclass correlation coefficient. Specifically, we will compare energy expenditure in MET*min/week (IPAQ) or MET*hour/week (CHAMPS) to that measured by the Actigraph accelerometer over the course of a week. For preference, we will compare subjects scores as indicated on the bidirectional scale to their necessity-harm differential as calculated by the Belief Screen of the BMQ using Spearman correlation coefficient. Contingency analyses tables will be used to determine the sensitivity and specificity of the bidirectional preference scale and the necessity-harm differential (as calculated on the Belief Screen) that best discriminates between those with preference for medication and those without. Discriminant validity, the ability to distinguish between populations, will be determined by comparing mean differences in energy expenditure for each physical activity instrument between responders and non-responders to anticholinergic medication as defined by the PGI-I. We will compare total MET*min/week (IPAQ) or MET*hour/week (CHAMPS), as well as energy spent in sedentary and moderate-to-vigorous physical activities (CHAMPS) between responders and non-responders using Wilcoxon rank sum test. For preference, we will compare the BMQ Belief necessity-harm differential and bidirectional preference scale score using Wilcoxon rank sum test. Responsiveness, the ability of the instruments to detect clinically meaningful change, will be assessed. First, pretreatment energy expenditure and preference will be compared with post-treatment activity and preference scores, respectively, using the t-test. Next, effect size (change in mean score/SD of baseline) and standardized response mean (change in mean score/SD of the change) will be assessed. For both, values of 0.50.7 will be considered moderate responsiveness; 0.81, good; and 1, excellent. We will measure minimum clinically important difference (MCID); specifically, the smallest change in physical activity associated with clinically meaningful change in global rating scale (mean change in energy expenditure in subjects indicating a little better or greater in the global rating scale). Specific Aim 3: We will compare within subject change in physical activity from baseline to 8 weeks using the paired t-test. Improvement in physical activity will be defined as 15% increase in energy expenditure as compared to baseline. The effect of age, comorbidities, baseline activity, severity of cognitive impairment, BMI on physical activity will be examined using regression analysis. We will also compare change in activity, proportion of subjects

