
showing improvement in activity, adherence (80% or greater, as measured by pill count and MASRI), response to medication (PGI-I), overall quality of life (SF-12), neurocognitive and balance function (MMSE and Berg Balance Scale scores, respectively), and urinary symptoms (OABq-SF score) in adults expressing preference for medication to those expressing no preference. The effect of preference will be measured using regression analysis, with adjustment for baseline physical activity, Charlson co-morbidity index, age, and BMI.

The following documents are currently attached to this item:

There are no documents attached for this item.

Data confidentiality

- Paper-based records will be kept in a secure location and only be accessible to personnel involved in the study.
- Computer-based files will only be made available to personnel involved in the study through the use of access privileges and passwords.

Prior to access to any study-related information, personnel will be required to sign statements agreeing to protect the security and confidentiality of identifiable information.

- Wherever feasible, identifiers will be removed from study-related information.

A Certificate of Confidentiality will be obtained, because the research could place the subject at risk of criminal or civil liability or cause damage to the subject's financial standing, employability, or liability.

A waiver of documentation of consent is being requested, because the only link between the subject and the study would be the consent document and the primary risk is a breach of confidentiality. (This is not an option for FDA-regulated research.)

Precautions are in place to ensure the data is secure by using passwords and encryption, because the research involves web-based surveys.

Audio and/or video recordings will be transcribed and then destroyed to eliminate audible identification of subjects.

Subject Confidentiality

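### The Aim 3 preference regressions list one covariate set, without the outcome's own baseline for the non-activity outcomes measured at both visits, and without sex

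*Combined protocol and SAP*

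**What the plan says.** The Aim 3 paragraph of the Analysis Plan lists the comparisons between preference groups. It opens with "We will also compare change in activity, proportion of subjects" who improve, goes on to adherence, PGI-I, SF-12, and cognition and balance (named as MMSE and Berg), and ends with "and urinary symptoms (OABq-SF score) in adults expressing preference for medication to those expressing no preference".

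The next sentence says that the effect of preference will be estimated by regression "with adjustment for baseline physical activity, Charlson co-morbidity index, age, and BMI". No other section adds an outcome-specific baseline or sex. The other Aim 3 regression, on predictors of activity, also omits sex.

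Three other parts of the document bear on this:

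- **Visit schedules** (Design and Procedures): OABq-SF, SF-12, Mini-Cog and SPPB are collected at baseline and at 8 weeks. MMSE and Berg appear at neither visit. PGI-I, pill count and MASRI appear only at 8 weeks.
- **Accrual**: "We anticipate that the female:male ratio will be 2:1".
- **Design**: all subjects receive fesoterodine whatever their preference. Preference is the patient's own rating, not an allocation.

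**The concern.** Baseline physical activity is the natural baseline covariate for an activity outcome. For urinary symptoms or quality of life, the baseline of the same instrument would normally be the strongest predictor of the week-8 value, and the listed set does not contain it.

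Two things are at stake. The first is confounding. Patients sort themselves by preference, and symptom severity could plausibly influence that preference. If the groups start at different levels, part of the gap enters the estimated preference effect. Aim 3 hypothesises greater urinary improvement in those who prefer medication; if they start worse, an unadjusted change score could show that without any effect of preference. The second is precision. Aim 3 also hypothesises no difference in neurocognitive testing, and avoidable noise makes a non-significant result easier to obtain.

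Sex is known for every subject and could relate to both preference and outcome. The plan does not explain leaving it out.

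**Working it through.** **1. Which outcomes are affected.** Setting the outcome list beside the visit schedules:

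- Change in activity and proportion improved: own baseline already in the model. Not affected.
- Adherence and PGI-I: no pre-treatment value exists. Not affected.
- OABq-SF and SF-12: measured at both visits, own baseline not listed. Affected.
- Cognition and balance: affected if the scheduled Mini-Cog and SPPB are meant. For MMSE and Berg as named, no baseline is scheduled.

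**2. The plan's own figure.** Accrual states 90% power for Aim 3 with 80 subjects. That figure is for a difference in a proportion, gives no base rate and uses no covariates, so it neither supports nor contradicts this point. The usable input is the sample: 80 × (1 − 0.15) = 68 evaluable. The 50% preference rate assumed for Aim 2 makes that 34 per group.

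**3. Precision with equal SDs.** Let r be the correlation between baseline and week 8. The documents give no value, so it is assumed. In units of the outcome variance:

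| r | Week-8 score alone (1) | Change, 2(1 − r) | Own-baseline adjusted, 1 − r² | Adjusted ÷ change, (1 + r)/2 |
|---|---|---|---|---|
| 0.3 | 1 | 1.40 | 0.91 | 0.65 |
| 0.5 | 1 | 1.00 | 0.75 | 0.75 |
| 0.7 | 1 | 0.60 | 0.51 | 0.85 |

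At r = 0.5 and 34 per group, power for a 0.5 SD difference is 54% without the own baseline and 66% with it.

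**4. Precision with unequal SDs.** Entry requires high urgency on the OABq-SF, which may narrow its baseline spread. Let k = baseline SD ÷ week-8 SD. Then Var(change) = 1 + k² − 2rk, and Var(adjusted) stays 1 − r². With k = 0.7 (assumed):

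- r = 0.5: 0.75 ÷ 0.79 = 0.95. 68 ÷ 0.95 ≈ 72, so the gain is worth about 4 subjects.
- r = 0.7: 0.51 ÷ 0.51 = 1.00. No gain.

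With equal SDs the same calculation gives 68 ÷ 0.75 ≈ 91 and 68 ÷ 0.85 = 80, or about 23 and 12 subjects.

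**5. Bias if the groups differ at baseline.** Let d be the gap in SD units (assumed), with equal SDs and both groups regressing to a common mean. The bias is −(1 − r)d for change and +rd for the week-8 score. A simulation checked this with 34 per group, 4,000 runs, no true effect, baseline activity as the only planned covariate, and a correlation of 0.2 between it and the outcome's baseline. At d = 0.5:

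| r | Change: bias, type I error | Week-8: bias, type I error | Own baseline added: bias, type I error |
|---|---|---|---|
| 0.3 | −0.35, 22% | +0.15, 9% | 0.00, 5% |
| 0.5 | −0.25, 17% | +0.26, 17% | 0.00, 5% |
| 0.7 | −0.15, 11% | +0.35, 30% | 0.00, 5% |

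At d = 0 all three models stay near 5%.

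**6. Sex.** A 2:1 ratio means about a third of subjects are men. The documents give no association of sex with preference or with any outcome, so no bias or variance figure can be computed.

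**The case against.** The strongest reply is that the covariate sentence does not say it governs every outcome. A list led by baseline activity may have been written for the activity model alone. That is possible, but then the other outcomes have no stated model, and the remedy is the same.

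A reader might infer more than the text supports:

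- **That every Aim 3 outcome is adjusted for the wrong baseline.** Step 1 shows otherwise, and physical activity, the primary outcome, is handled correctly.
- **That regression to the mean will distort the comparison.** No baseline gap is documented. Entry selection on OABq-SF severity by itself affects both groups. If the week-8 score is modelled, the problem is baseline confounding with the opposite sign.
- **That the omission costs 12 to 23 subjects.** That range needs change scores and equal SDs. The Secondary outcome section does speak of changes in urinary symptoms and neurocognitive testing, but the Analysis Plan does not say which form is modelled for OABq-SF or SF-12.
- **That baseline activity belongs only in the activity models.** Removing it elsewhere would drop a planned confounder from a non-randomised comparison, and nothing in the documents justifies that.

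It is also fair to say that, for self-selected groups, change-score and baseline-adjusted analyses can answer different questions (Lord's paradox). If the groups have stably different levels, baseline adjustment can itself be biased. This limits the claim in step 5, and it is a reason to state the model in advance. Finally, these are secondary comparisons in an aim meant to give preliminary data.

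**Conclusion.** The point holds in a limited form. As written, the preference regressions omit the own baseline for OABq-SF and SF-12, and for Mini-Cog and SPPB if those are the intended instruments, and they omit sex throughout.

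Under equal SDs, adding the own baseline brings the variance to 0.75 to 0.85 of the change-score variance at r = 0.5 to 0.7. For OABq-SF with a compressed baseline the gain could be close to nothing. The bias is conditional: with an assumed 0.5 SD gap and r = 0.5 it is about 0.25 SD in either direction, with type I error near 17%; with no gap there is none. The correlation, the SD ratio and the gap are all assumptions. Own-baseline adjustment removes this bias only if no other confounder remains and the groups share a common mean. The case for sex rests on its availability and low cost, not on a computed effect.

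The change is worth making because the data are already collected and the plan already does this for activity. It does not call the primary activity analysis into question.

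**What to change.** In the Aim 3 paragraph, state that for each continuous outcome with a baseline value, the week-8 value will be regressed on preference, that outcome's own baseline and sex, together with all the planned covariates: baseline physical activity, Charlson index, age and BMI. In the activity models the own baseline is already present, so only sex is added. Say explicitly which outcomes the covariate list covers.

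Before that, reconcile MMSE and Berg in the Analysis Plan with Mini-Cog and SPPB in the visit schedules, since an own-baseline model cannot be fitted to an instrument that is not administered.

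The cost is a sentence or two of text and no new measurements. With one term per covariate, the planned model has 6 parameters including the intercept, leaving 68 − 6 = 62 residual degrees of freedom. Two more terms leave 60.
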